19.1. Statistical Plan Overview

The study will be conducted with two separate strata (pigment, wrinkles) which will be evaluated. Benign pigmented lesions including dyschromia (Group A) and wrinkles including fine lines (Group B) will be separately powered and analyzed for efficacy and safety while both groups will further be combined for safety analyses. All study sites will be eligible to enroll subjects into each stratum; no subject will be enrolled into both strata.

Subjects participating in the pigment treatment stratum will be evaluated using the Pigment Clearance Score (Appendix A) while subjects participating in the wrinkle treatment stratum will be evaluated using the Fitzpatrick Wrinkle Score (Appendix B). All study subjects will also be evaluated using the Subject Pain Scale (Appendix C), Subject Satisfaction Survey (Appendix D), the Local Skin Response (Appendix E), and will be evaluated for safety according to 21 CFR Part 812 as well as ICH guidelines (E3 and E6) and ISO 14385:2016 as applicable.

A statistical analysis plan (SAP) will be finalized prior to study initiation. The database will be constructed using Microsoft Office Excel (Microsoft, Redmond, WA). The database will be locked following a review of all protocol deviations to be classified as a major or minor deviation. Major and minor protocol deviations will be reviewed once all data undergo source document verification and prior to database lock. The independent biostatistician will determine major vs. minor protocol deviations.

Data analyses will be performed using SAS Version 9.3 or later (SAS Institute, Cary NC) and StatXact Version 10 or later (StatXact, Cambridge MA). All analyses will be performed in a GCP environment controlled by SOPs.

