28.	Publication Policy.....	29
29.	References	30
30.	Appendices.....	31
30.1.	Appendix A: Pigment Clearance Score Pigment Score	32
30.2.	Appendix B: Fitzpatrick Wrinkle Score (FWS)	33
30.3.	Appendix C: Subject Pain Scale	34
30.4.	Appendix D: Subject Satisfaction Scale	35
30.5.	Appendix E: Local Skin Response	36

1. Study Synopsis

Protocol Number	PWY18010
Protocol Version	v 1.0 28NOV2018
Protocol Title	Evaluation of the PicoWay® Laser System with 730 nm and Resolve™ Fusion Handpieces for Treatment of Benign Pigmented Lesions and Wrinkles
Short Title	PicoWay 730 Resolve Fusion
Device Description	PicoWay® Laser System, Candela Corporation, Wayland, MA
Study Design	Prospective, non-randomized, multi-center, evaluator blinded, safety and efficacy clinical study
Study Objective	Evaluate the safety and efficacy of the PicoWay® Laser System with 730 nm and Resolve™ Fusion handpieces for treatment of benign pigmented lesions including dyschromia, and wrinkles including fine lines
Investigative Sites	Up to two (2) investigational sites located in the United States
Number of Subjects	Up to 160 subjects
Study Duration	The overall duration of this study is not expected to exceed 24 months
Study Overview	
Upon enrollment subjects will be assigned to one or possibly both of the following laser treatment groups based on their qualifying indications:
 
Group A: Benign Pigmented Lesions including dyschromia Group B: Wrinkles including fine lines
 
Subjects will receive up to 4 laser treatments at 6 ± 2 week intervals with the PicoWay® Laser System. Handpiece selection and specific treatment parameters will be determined by the clinician.
 
The treatment area will be photographed at every visit. Baseline photographs will be compared to follow-up photographs to determine the effectiveness of the laser treatments.
 
The Study Doctor or staff will contact subjects by telephone 10 days after each treatment visit to assess healing response.
 
Optional skin punch biopsies may be collected prior to or immediately after laser treatment, or at follow-up visits at clinician's discretion.
 
Subjects must provide signed written consent prior to any biopsy procedure. Subjects may still participate in the study if they choose not to undergo biopsies.
 
Subjects will be scheduled for follow-up visits at 4 ± 1 week, 8 ± 2 weeks and 12 ± 2 weeks after the final laser treatment. Additional visits may be requested at the discretion of the clinician.

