Study Population	
Adults seeking treatment of benign pigmented lesions including dyschromia and/or wrinkles including fine lines, and who satisfy all study inclusion and exclusion criteria, and who provide written informed consent will be considered eligible for this study.

Study Eligibility	
Inclusion Criteria
 
Subjects must meet all inclusion criteria to be enrolled in this study:
 
 1. Willing to provide signed informed consent 2. Adults age 21 to 80 3. Fitzpatrick Skin Type (FST) I to VI 4. Presence of benign pigmented Lesions assessed at baseline as Pigment Severity Score (PSS) of "2" or higher and/or wrinkles assessed at baseline as Fitzpatrick Wrinkle Score (FWS) of "2" or higher 5. Willing to allow photographs and/or video to be taken of treated areas for the purposes of this research study 6. Willing to abstain from any other procedures for treatment of benign pigmented lesions or wrinkles in the laser treatment areas for the duration of the study including surgery, light, laser, ultrasound or radiofrequency treatments 7. Willing to abstain from use of prescription cosmetic products for treatment of benign pigmented lesions or wrinkles in the laser treatment areas for the duration of the study including injections of neurotoxins or dermal fillers, skin lightening creams, and wrinkle creams 8. Willingness to adhere to study treatment and follow-up visit schedules 
Exclusion Criteria
 
Subjects who meet any exclusion criteria cannot be enrolled in the study:
 
 1. Pregnant, planning pregnancy or breast feeding 2. Allergy to topical or injectable lidocaine or similar medications 3. Allergy to topical steroid or similar medications 4. Unprotected sun exposure in the six weeks prior to enrollment, or active tan in the laser treatment area 5. History of melanoma in the intended treatment area 6. History of keloid or hypertrophic scar formation 7. Use of topical or systemic retinoid therapy during the past six (6) months 8. Use of neurotoxins in the intended treatment area within the past three (3) months or throughout the duration of the study 9. Use of dermal fillers in the intended treatment area within the last six (6) months or throughout the duration of the study

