After successful completion of the 12 week follow-up visit, subjects will be exited from the study.

7. Study Population

Up to 160 subjects will be enrolled in this study at up to two (2) investigational sites in the United States.

The Study Population will be enrolled at the discretion of the Investigator after determining that eligible subjects have unwanted benign pigmented lesions including dyschromia on the face, scalp, neck, chest, back, arms, hands, legs or feet; or wrinkles including fine lines on the face.

[figure not shown]
Subjects will be assessed at the Screening Visit and allocated to one **or both** study sub-groups if eligible:

Group A: Benign Pigmented Lesions including dyschromia

Group B: Wrinkles including fine lines

The logic scheme used for group allocation is provided below in Figure 1.

Figure 1: Study Group Allocation Logic

All subjects must satisfy the inclusion and exclusion criteria and provide signed informed consent to be eligible for participation in the study. Subjects enrolled in the study can discontinue their participation at any time for any reason without prejudice or reduction in the quality of their medical care. The Investigator or Sponsor can terminate a subject's participation in this study at any time to protect the subject's health or if a subject fails to

follow directions that result in noncompliance with study procedures. Subjects who withdraw or are terminated from the study prior to completion may be replaced.

8. Inclusion / Exclusion Criteria

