19.5. Safety Analyses

Safety will be evaluated using the Local Skin Response (Appendix E) which will specifically assess the following nine pre-defined safety endpoints: erythema, edema, whitening, petechiae, pinpoint bleeding, purpura, crusting, blistering, burn, as well as other to be graded on a 5-point ordinal score.

Safety will be evaluated in the Intent to Treat (ITT) population which includes all treated subjects. Safety results will be displayed separately for Groups A and Group B. Analyses will include a summary of the incidence, severity, and relatedness of all reported local skin responses, adverse device effects, and unanticipated adverse device effects. In addition, the percentage with no adverse device effects will also be reported as well as the percentage according to worst overall degree; a similar evaluation will be performed for the worst degree for those at least related to the study treatment. The percent reporting each ordinal score per safety endpoint will be presented separately for each stratum and combined.

20. Histological Analysis

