30.5. Appendix E: Local Skin Response

Local Skin Response Assessment				
 None  N/A				
 Erythema	 Edema	 Whitening	 Petechiae	 Pinpoint Bleeding
 None  Trace  Mild  Moderate  Severe	 None  Trace  Mild  Moderate  Severe	 None  Trace  Mild  Moderate  Severe	 None  Trace  Mild  Moderate  Severe	 None  Trace  Mild  Moderate  Severe
 Purpura	 Crusting	 Blister	 Burn	 Other:
 None  Trace  Mild  Moderate  Severe	 None  Trace  Mild  Moderate  Severe	 None  Trace  Mild  Moderate  Severe	 None  Trace  Mild  Moderate  Severe	 None  Trace  Mild  Moderate  Severe
 Other:	 Other:	 Other: _____	 Other: _____	 Other:

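### Section 19.1 bars enrolment in both strata while the synopsis and Section 7 allow it, and the combined safety percentages have no counting rule for a subject in both groups

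*Combined protocol and SAP*

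**What the plan says.** The enrolment sections allow dual membership. The synopsis, under Study Overview, states: "Upon enrollment subjects will be assigned to one or possibly both of the following laser treatment groups based on their qualifying indications". Section 7 says subjects are "allocated to one or both study sub-groups if eligible". The synopsis describes the population as "Adults seeking treatment of benign pigmented lesions including dyschromia and/or wrinkles including fine lines".

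The statistical section does not allow it. Section 19.1 defines two strata, pigment (Group A) and wrinkles (Group B), and says "no subject will be enrolled into both strata".

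Section 19.1 also pools the two groups for safety. Section 19.5 says that the percentage at each grade of each local skin response "will be presented separately for each stratum and combined". The safety population there is every treated subject. The synopsis instead relates adverse device effects to the number of laser treatments given. Section 19.4 displays pain and satisfaction by group and runs the effectiveness analyses on a Per Protocol set that drops major deviations. Under Section 19.1 the independent biostatistician decides which deviations are major, after source verification and before database lock.

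**The concern.** The strata in Section 19.1 are Groups A and B, so the two rules govern the same units. The statistical section is written as if dual subjects did not exist, and the enrolment sections can create them. Three things are then undefined.

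- **Deviation status.** A subject correctly enrolled under Sections 1 and 7 contravenes Section 19.1. If that were classed as a major deviation, the subject would leave the Per Protocol set. Nothing says how it would be classed, and the decision falls late, when data are in hand.
- **Evaluable counts.** It is not stated whether one dual subject counts toward both the 30 in Group A and the 34 in Group B.
- **Combined safety and group-wise tables.** No rule says how a dual subject enters the combined percentages, or whether one session treating both indications is one treatment or two. The pain and skin-response forms have no place to say which indication an answer belongs to.

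**Working it through.** **1. The rules side by side.** The synopsis permits one or both groups, as does Section 7. Section 19.1 permits one only. Figure 1, the allocation logic, is not available in the text, but the sentences that introduce it say one or both. No other text resolves the conflict.

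**2. The plan's own sample sizes (Section 19.3).**

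- Group A: n = 30, 50% against 75%, two-sided exact binomial test at 5%. The smallest r with 2 × P(X ≥ r | 30, 0.50) ≤ 0.05 is 21, where the doubled tail is 0.0428 (it is 0.0987 at r = 20). Power is P(X ≥ 21 | 30, 0.75) = 0.803.
- Group B: n = 34, difference 1 point, SD 2 points, two-sided paired t-test at 5%. Non-centrality is (1/2) × √34 = 2.92 on 33 degrees of freedom. Power is 0.808.

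Both stated figures reproduce. Each uses only its own group, so overlap changes neither.

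**3. People behind the group records.** Let m be the number of subjects in both groups. The documents give no value, so I take its full range, 0 to 30, as an assumption. Records = 30 + 34 = 64 and people = 64 − m.

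**4. Effect on a combined percentage if records were stacked.** Suppose e people have a given response and d of them are recorded with it under both groups. The stacked percentage is (e + d)/64 and the per-person percentage is e/(64 − m). Their ratio is (1 + d/e) × (64 − m)/64. With d/e between 0 and 1:

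| m | People | Records | Stacked ÷ per-person |
|---|---|---|---|
| 0 | 64 | 64 | 1.00 |
| 10 | 54 | 64 | 0.84 to 1.69 |
| 20 | 44 | 64 | 0.69 to 1.38 |
| 30 | 34 | 64 | 0.53 to 1.06 |

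The lower end applies when nobody's response is recorded under both groups. The upper end applies when everyone with the response is a dual subject recorded under both. The ratio is 1 when d/e = m/(64 − m), so the direction of any error cannot be known in advance.

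The 30 and 34 are evaluable efficacy targets, and the safety set is larger. At the cap of 160 people, stacking would give 160 + m records, from 160 to 320.

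**5. Attribution on the forms.** Appendix C asks one question about pain during that day's treatment. Appendix E has no group or area field. Appendix D asks only about pigment improvement, so no Group B subject, dual or not, is asked about wrinkles. Section 10.2 does record treatment location and handpiece, but these identify the indication only in part. The 1064 nm Resolve Fusion handpiece is listed for both conditions, and Section 7 allows both conditions on the face.

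**The case against.** The best reply is that the conflict need never arise and that the safety consequence is assumed rather than planned. Much of that stands, and it limits what can be claimed.

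- A reader might infer that sites cannot comply with all three sections. The documents do not support that. The dual option is permissive, so a site that places each subject in one group satisfies every section. The breach occurs only when the option is used.
- A reader might infer that double counting is built in. It is not. Section 6 gives each subject one identifier on all records, the safety set in Section 19.5 consists of subjects, and its worst-degree summary is naturally per person. Counting once is feasible but is nowhere required for the combined skin-response percentages.
- A reader might infer that safety intervals would be too narrow, for example by √(34/64) = 0.73, or that a zero-event upper 95% limit would read 5.6% instead of 10.3%. Section 19.5 plans percentages and no intervals. Those figures would also apply efficacy targets to the safety set, under maximal overlap and with second records that add no information.
- A reader might infer that responses cannot be attributed to a group at all. Location and handpiece are recorded, and the full case report form layout is not in the documents. The supportable claim is that the forms shown do not link a pain or skin-response grade to an indication.

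Section 19.1 also promises a finalized statistical analysis plan before the study starts. That could supply a counting rule, but it would not by itself remove a contradiction between protocol sections about who may be enrolled.

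**Conclusion.** The contradiction is explicit, concerns the same two groups, and is unresolved in the current text. It leaves open a dual subject's deviation status, Per Protocol membership and contribution to the evaluable counts. It also leaves the combined safety percentages without a counting rule.

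The size depends on a quantity that the documents do not give. The effect is nil if Section 19.1 is enforced. If dual enrolment occurs and records are stacked, 64 group records could stand for 34 to 64 people, and the combined percentages would have the wrong denominator. Power within each group is unaffected, and I make no claim about interval width. Severity: should-fix.

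**What to change.** Reconcile Sections 1, 7 and 19.1 to one enrolment rule. If the strata are to be exclusive, remove the dual option from Sections 1 and 7 and say how a subject who qualifies for both is allocated.

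If dual enrolment stays:

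- delete the Section 19.1 sentence;
- state that a dual subject counts in each group's own analysis and that dual membership is not a deviation;
- state in Section 19.5 that each person counts once, at worst grade, in combined per-subject safety percentages;
- for the per-treatment denominator in the synopsis, state whether a session treating both indications is one treatment or two;
- record the treated indication or area with each pain and local skin response entry.

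Under either rule, Appendix D needs wrinkle wording. With dual enrolment it should ask about pigment and wrinkles separately, so that the group-wise tables in Section 19.4 can be built.

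The cost is wording changes plus an added field or question on the forms, with no extra subjects. The form changes should precede first treatment, because unattributed answers may not be recoverable later.

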19.2. Hypotheses

Null and alternative hypotheses are stratum specific. They assess the change from Baseline to Week 12/study exit.

Pigment effectiveness (5-point ordinal scale, 5 is best) will be evaluated according to the following null and alternative hypotheses for Group A:

- Null Hypothesis: Less than 50% experience good to excellent improvement in the Pigment Clearance Score (PCS)
- Alternative Hypothesis: At least 80% experience good to excellent improvement in PIS.

Fitzpatrick Wrinkle Score (9-point ordinal scale, 1 is best) will be evaluated separately for peri-orbital wrinkles and peri-oral wrinkles as well as the sum according to the following null and alternative hypotheses for Group B:

- Null Hypothesis: There is no mean improvement in the Fitzpatrick Wrinkle Score (FWS)
- Alternative Hypothesis: There is at least a 2-point mean improvement in FWS.

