17.1. Primary Effectiveness Endpoints

Benign Pigmented Lesions

Mean difference from Baseline to final 12-Week follow-up visit in Pigment Clearance Score as determined by blinded evaluators from clinical photographs.

Wrinkles

Mean difference from Baseline to final 12-Week follow-up in Fitzpatrick Wrinkle Score as determined by blinded evaluators from clinical photographs.

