19.3. Sample Size

The following summarizes the sample size required to achieve 80% power separately for pigmentation Group A and Group B for their respective primary efficacy endpoints.

From Kung, et al, 2018, Graph 1 indicates that for clearance of pigmentation, 0% experienced complete improvement (Grade 5: >95%), 53.8% experienced excellent (Grade 4: 75-94%) improvement, while 30.8% experienced good (Grade 3: 50-74%) improvement from baseline. With 30 evaluable subjects, there is 80% power to reject a 50% improvement rate in favor of a 75% improvement rate according to a two-sided exact binomial test with 5% Type I error. Statistical significance will be achieved if █% improvement is observed at 12 week follow-up / study exit visit.

From Fitzpatrick, et al, 1996, Table 2 indicates for peri-orbital and peri-oral wrinkles, the mean changes from baseline to study exit were 2.34 points and 2.25 points with standard deviations < 2 points. With 34 evaluable subjects, there is 80% power to detect a 1-point improvement from baseline according to a two-sided paired t-test with 5% Type I error. Statistical significance will be achieved if a █ mean improvement is observed from Baseline to 12 week follow-up / study exit with a 2-point standard deviation.

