19.4. Effectiveness Analyses

The skin pigmentation score will be evaluated using a paired t-test separately for the peri-orbital, peri-oral, and combined outcomes from baseline to study exit. In addition, the percentage achieving a 1-point improvement will also be displayed with two-sided 95% confidence intervals to support regulatory submissions requiring 1-point improvement analyses.

Wrinkle score improvement will be evaluated using a two-sided exact binomial test.

The Subject Pain Scale and Subject Satisfaction Score will be evaluated by displaying the distributions with the range, mean, and two-sided 95% confidence intervals provided. Results will be displayed separately for Groups A and Group B.

The effectiveness analyses will be performed using a Per Protocol (PP) population which excludes subjects with major protocol deviations such as subjects withdrawn prior to final evaluation.

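### The alternatives in 19.2 (at least 80% responders, at least 2 FWS points) are not the effects that 19.3 powers for (75%, 1 point), and neither value is tested, so significance does not establish them.

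*Combined protocol and SAP*

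**What the plan says.** Section 19.2 gives each group a null and an alternative.

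- **Group A (pigment).** The null is a good-to-excellent responder rate below 50%. The alternative reads: "Alternative Hypothesis: At least 80% experience good to excellent improvement in PIS". (PIS appears to be the pigment score called PCS elsewhere; the list of appendices in section 30 uses the PIS name for Appendix A.)
- **Group B (wrinkles).** The null is no mean improvement in FWS. The alternative reads: "Alternative Hypothesis: There is at least a 2-point mean improvement in FWS".

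Section 19.3 sizes each group on a smaller effect.

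- **Group A.** With 30 evaluable subjects and a two-sided exact binomial test at 5%, "there is 80% power to reject a 50% improvement rate in favor of a 75% improvement rate".
- **Group B.** Using a two-sided paired t-test at 5% and an SD of 2 points: "With 34 evaluable subjects, there is 80% power to detect a 1-point improvement from baseline".

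Section 19.3 also cites prior results. For pigment, "53.8% experienced excellent (Grade 4: 75-94%) improvement, while 30.8% experienced good (Grade 3: 50-74%) improvement from baseline". For wrinkles, "the mean changes from baseline to study exit were 2.34 points and 2.25 points", with SDs below 2.

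Nothing in 19.2 to 19.4 tests against 80% or 2 points, ties a confidence limit or point estimate to them, or explains why they differ from the 19.3 values.

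**The concern.** A stated alternative tells the reader what will be concluded if the null is rejected. Here the alternatives are much stronger than anything the tests examine. Rates from 50% to below 80%, and mean improvements above zero but below 2 points, belong to neither hypothesis, yet the trial is sized for effects inside those gaps.

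What is at stake is the claim attached to a positive result. A significant test could be read as support for 80% or 2 points when it shows only a rate above 50% or a mean improvement above zero. The study is single-arm, with subjects as their own controls, and 19.4 says some analyses are meant to support regulatory submissions. The claim should therefore be fixed before the data are seen.

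**Working it through.** The significance thresholds in 19.3 are blacked out, so they are recomputed here from the stated inputs.

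**Group A: n = 30, null rate 0.50, two-sided exact binomial, 5%.**

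1. Critical value. Two-sided p = 2·P(X ≥ r | 30, 0.5). At r = 20, p = 0.099; at r = 21, p = 0.043. Significance starts at 21/30 = 70%.
2. Stated power. P(X ≥ 21 | 30, 0.75) = 80.3%, which reproduces the plan's 80%. At a true rate of 80% it is 93.9%.
3. What the result supports (Clopper-Pearson 95% intervals):

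| Observed | 95% CI |
|---|---|
| 21/30 = 70% | 50.6% to 85.3% |
| 24/30 = 80% | 61.4% to 92.3% |
| 28/30 = 93.3% | lower limit 77.9% |
| 29/30 = 96.7% | lower limit 82.8% |

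The smallest significant result is an observed rate below both 75% and 80%. If the true rate is 75%, outside the stated alternative, the test is still significant 80.3% of the time. A lower limit above 80% needs 29/30.

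**Group B: n = 34, null mean 0, SD of change 2, two-sided paired t-test, 5%.**

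1. Standard error = 2/√34 = 0.343. With t(0.975, 33) = 2.0345, the 95% half-width is 2.0345 × 0.343 = 0.698.
2. Critical mean. Significance starts at an observed mean of about 0.70, with CI about 0 to 1.40. If the observed SD were 1.5 or 2.5, the critical mean would be 0.52 or 0.87.
3. Stated power. Noncentral t, 33 df, noncentrality (1/2)·√34 = 2.92, gives 80.8%, again as stated. At 2 points power is 99.99%.
4. What the result supports:

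| Observed mean (SD 2) | 95% CI |
|---|---|
| 0.70 | about 0 to 1.40 |
| 1.0 | 0.30 to 1.70 |
| 2.0 | 1.30 to 2.70 |
| 2.70 | lower limit 2.0 |

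An observed mean of 1.0 is significant against zero and also significantly below 2: t = (1 − 2)/0.343 = −2.92, p = 0.006. The null would be rejected by data that contradict the stated alternative.

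**Where 80% and 2 points may come from.** The cited pigment results add to 53.8% + 30.8% = 84.6%, and the cited wrinkle means are 2.34 and 2.25. The 19.2 values sit just below these, so they may be expected values.

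**If 80% or 2 points had to be shown by the lower 95% limit.** No passage sets such a rule; this only shows what it would demand.

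- Group A: P(X ≥ 29 | 30, 0.846) = 4.3%.
- Group B, SD 2: the chance that the lower limit reaches 2 is 10.5% at a true mean of 2.25 and 15.9% at 2.34.

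**The case against.** The strongest reply is that nothing operative is wrong. Section 19.3 says which rate is rejected, and names the test, sidedness and error rate. It also gives an observed result at which significance is reached, blacked out here but present in the plan. Powering below the expected effect is conservative. Writing an anticipated effect as the alternative is loose but recognisable, and the cited results make that reading plausible. On this view the harm is only a possible misreading.

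Much of this stands. No figure is miscalculated and there is no power shortfall. The lower-limit probabilities also depend on the rule chosen. If 80% or 2 points had only to be reached by the point estimate, a rule equally absent from the plan, the chances at the prior-study results would be about 83% for Group A (at least 24/30) and 77% to 84% for Group B (SD 2). With an SD of 1.5, the Group B lower-limit figures rise to about 15% to 25%.

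There is a further caveat for Group B. Section 19.2 applies its hypotheses to peri-orbital wrinkles, peri-oral wrinkles and their sum, and neither section says which outcome its 2 points or 1 point describes. The prior means are given per region, so comparing the two values is reasonable, but the text does not settle it.

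None of this removes the inconsistency. Section 19.2 labels 80% and 2 points as alternative hypotheses, not expectations, and no passage corrects that.

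**Conclusion.** The concern holds. The hypotheses and the sample size name different effects, and the tests bear on neither 80% nor 2 points. Significance can be reached from an observed 70% in Group A and from about 0.70 points in Group B. In Group B that smallest significant result is incompatible with a 2-point mean.

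The Group A figures rest on n = 30 and the exact test described in 19.3. The Group B figures rest on n = 34, an observed SD of 2, and one FWS outcome being meant in both sections. This is a defect in the stated hypotheses and in the conclusion drawn from them. It should be fixed, but it does not put the sample size in doubt.

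**What to change.** Restate 19.2 to agree with the two-sided tests in 19.3.

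- **Group A:** null rate equal to 50%, alternative not equal to 50%, benefit concluded if above 50%; 75% labelled as the design effect. Keeping the existing directional null and stating its complement would also work.
- **Group B:** null mean improvement of zero, alternative not zero, benefit concluded if positive; 1 point with SD 2 labelled as the design effect. Say which outcome (each region or the sum) it refers to.
- State that significance supports only a rate above 50% and a mean improvement above zero, and report each estimate with its 95% CI.
- If 80% and 2 points are kept, call them expected values or targets. If they are meant as success criteria, add an explicit rule, for example on the lower confidence limit, and size the trial for it.

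Two neighbouring passages need aligning in the same edit, because rewording 19.2 alone will not reconcile them. Section 19.4 reverses the tests in 19.3: it gives the paired t-test to pigmentation, and "Wrinkle score improvement will be evaluated using a two-sided exact binomial test". Section 17.1 makes the Group A primary endpoint a mean, "Mean difference from Baseline to final 12-Week follow-up visit in Pigment Clearance Score", whereas 19.2 and 19.3 test a responder rate. The Group A wording above assumes the responder rate is the primary hypothesis, so that choice has to be settled first.

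The cost is protocol and SAP wording. The sizes of 30 and 34 stay unless 80% or 2 points becomes a success criterion. The drawback for the sponsor is a more modest claim from a positive test.

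### Section 19.4 swaps the two primary tests relative to 19.3, and 19.2 puts three wrinkle outcomes under one hypothesis pair without saying which decides

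*Combined protocol and SAP*

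**What the plan says.** **Endpoint.** Section 17.1 gives one primary wrinkle endpoint, with no facial region: "Mean difference from Baseline to final 12-Week follow-up in Fitzpatrick Wrinkle Score".

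**Hypotheses.** For Group B, section 19.2 says that the FWS "will be evaluated separately for peri-orbital wrinkles and peri-oral wrinkles as well as the sum according to the following null and alternative hypotheses". One null (no mean improvement) and one alternative (2 points or more) cover all three outcomes.

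**Sample size.** Section 19.3 sizes one two-sided paired t-test at 5%: "With 34 evaluable subjects, there is 80% power to detect a 1-point improvement from baseline". Its success statement refers to a "mean improvement is observed from Baseline to 12 week follow-up / study exit with a 2-point standard deviation"; the threshold itself is blacked out. The supporting data are regional: "mean changes from baseline to study exit were 2.34 points and 2.25 points with standard deviations < 2 points". For pigment, 19.3 sizes a two-sided exact binomial test of a 50% rate against 75%, with 30 evaluable subjects.

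**Analysis.** Section 19.4 reads: "The skin pigmentation score will be evaluated using a paired t-test separately for the peri-orbital, peri-oral, and combined outcomes". It continues, for Group B: "Wrinkle score improvement will be evaluated using a two-sided exact binomial test".

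**SAP.** Section 19.1 adds: "A statistical analysis plan (SAP) will be finalized prior to study initiation". The supplied text contains no further rule for the three FWS outcomes.

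**The concern.** There are two linked problems.

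**The tests are reversed.** Section 19.3 pairs the binomial test with pigment and the t-test with wrinkles; 19.4 does the opposite. An analyst who follows 19.4 has no t-test for the mean FWS change and no binomial test for the pigment rate. The regional pigment analysis also cannot be done for many Group A subjects, because section 7 admits lesions on the back, legs or feet.

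**There is no deciding rule for Group B.** Three outcomes share one hypothesis pair, and the text does not say whether one named outcome, any one, or all three must succeed. Error rate and power both depend on that answer. If it is settled after the data are seen, the choice among three results is open. The regions also appear only in 19.2 to 19.4. Section 7 requires only facial wrinkles, and 10.1 records an FWS without regions, so it is unclear how a subject with one affected region enters a regional test or the sum.

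**Working it through.** **1. Reproduce 19.3.**
- Group B: n = 34, mean 1 point, SD 2, two-sided 5%. Noncentrality = (1/2) × √34 = 2.92 on 33 df; critical t = 2.035. Power = 80.8%. The plan's figure stands for one test on an outcome with SD 2.
- Group A: n = 30, null 50%. P(21 or more of 30 | 50%) = 0.0214, so the two-sided p is 0.043 and the null is rejected at 21/30. P(21 or more | 75%) = 80.3%. This figure also stands.

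So 19.3 describes a t-test on FWS and a binomial test on the pigment rate, and both calculations are sound.

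**2. Set 19.3 beside 19.4.**

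| Outcome | 19.3 | 19.4 |
|---|---|---|
| Pigment | exact binomial, n = 30 | paired t-test by peri-orbital, peri-oral, combined |
| Wrinkles | paired t-test, n = 34 | exact binomial |

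Peri-orbital and peri-oral are wrinkle regions in 19.2 and 19.3. The pigment sentence in 19.4 is also followed by a percentage with 1-point improvement, which matches the wrinkle responder endpoint in 17.3. The outcome names look transposed.

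**3. Error and power by decision rule.** Assumptions: all 34 subjects scored in both regions; SD 2 per region (the planning value in 19.3); bivariate normal changes; between-region correlation ρ from 0 to 0.9, which the documents do not give. Simulated paired t-tests on region 1, region 2 and their sum:

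| Rule at two-sided 5% per test | ρ = 0 | ρ = 0.5 | ρ = 0.9 |
|---|---|---|---|
| Any one, two-sided error | about 11.6% | about 9.8% | about 7.2% |
| Any one, error in the favourable direction (nominal 2.5%) | 5.9% | 4.9% | 3.6% |
| All three, power at 1 point per region | about 65% | about 70% | about 76% |

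Check at ρ = 0: the all-three power is close to 0.808² = 0.652. At the 2 points per region of 19.2, all-three power exceeds 99.9%. One named region keeps 5% error and 80.8% power if all 34 contribute to it.

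**4. The sum.** SD of the sum = 2 × √(2(1 + ρ)), which is 2.83 at ρ = 0 and 3.90 at ρ = 0.9.
- Power at n = 34 for 1 point on the sum: 52% (ρ = 0) to 31% (ρ = 0.9).
- Power for 2 points on the sum: 98% to 83%.
- Smallest significant mean = 2.035 × SD/√34: 0.70 for one region, 0.99 to 1.36 for the sum. These are reconstructions, since the plan's own threshold is blacked out.

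The set of 1 point, SD 2 and n = 34 therefore describes one outcome with SD 2, such as a single region, and not the sum.

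**The case against.** **The reversal is obvious and 19.3 shows the right pairing.** True: a regional pigment analysis makes little sense on its face. But 19.4 is the section that prescribes the analysis. The binomial sentence could be meant for the secondary wrinkle responder rate in 17.3. Even so, FWS would have no t-test and pigment no binomial test.

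**A reader might infer that 19.4 puts the wrong test on both primary endpoints.** For wrinkles that holds. For pigment it is unsettled: 17.1 makes the mean Pigment Clearance Score (PCS) difference primary and 17.3 makes the responder rate secondary, whereas 19.2 and 19.3 test and size the rate. A t-test suits a mean difference. What can be said is that 19.4 omits the pigment analysis that was sized.

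**A reader might infer that wrinkle error is inflated to about 12%.** The documents do not support that. It needs an unadjusted any-one rule, which nobody has stated, and the SAP promised in 19.1 may set a different one.

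**Each region may be its own claim.** Evaluating the regions separately allows this reading, and each claim would then keep 5% error and 80.8% power. The single FWS endpoint in 17.1 weighs against it.

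**The power loss is narrow.** This stands. It requires an all-three rule and a true effect near 1 point with SD 2. The cited regional changes are 2.34 and 2.25 points with SDs below 2. Nor does 19.3 say that its figures apply to the sum.

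**Conclusion.** The point holds in two parts. First, 19.4 as written contradicts 19.3 and, taken literally, omits the t-test for the FWS primary and the binomial test sized for pigment. This rests on the text alone. Second, 19.2 tests three FWS outcomes where 17.1 names one and 19.3 sizes one, with no deciding rule in the supplied text. The stated 5% and 80% are right for one test on an outcome with SD 2; under other rules they need not hold. The ranges in the working depend on SD 2 per region, complete scoring of both regions and an assumed correlation. They show what is left open, not what the trial will incur. The design is not shown to be underpowered or its error rate inflated. The plan should be corrected before analysis.

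**What to change.** 1. In 19.4, attach the paired t-test to FWS and the exact binomial test to the pigment responder rate. Make 17.1 and 17.3 agree with the rate tested and sized in 19.2 and 19.3.
2. In 19.2 and the SAP, name one deciding FWS outcome, tested once at two-sided 5%: the undivided FWS of 17.1, one region, or the sum. The undivided score matches 17.1 and 10.1 and avoids the one-region problem. Tie the n and SD in 19.3 to the chosen outcome; if it is the sum, restate the effect and SD. Report the other FWS outcomes as supportive with 95% confidence intervals, or test them in a fixed sequence after the deciding one.
3. If a region or the sum is chosen, state how subjects with one affected region enter, and have the blinded evaluators' form capture regional scores.

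**Cost.** Mostly wording, with no added visits. The scoring form may need a small change under item 3. n = 34 stands for an outcome with SD 2; for the sum it must be rechecked against the effect chosen. The price is that the remaining FWS outcomes become supportive or conditional.
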